#### 2.6.2. Final Analyses and Reporting

All final analyses identified in this SAP will be performed after the last subject has completed the study. This SAP and any corresponding amendments will be approved before database lock. Any supportive analyses which were not identified in the final approved version of this SAP (and prior to unblinding of statisticians) will be documented as exploratory in the CSR.

## 3. ANALYSIS SETS

There will be a single analysis set defined for this study: the Treated Analysis Set, which will include all subjects who receive at least 1 of the 4 study injections. All analyses will be performed according to treatment group received, even if the result of a randomization or

Local Tolerability Study - Contraception Statistical Analysis Plan Version 2.0 TV46046-WH-10147 /1191167 allocation error. During the study, several subjects reported receiving partial injections due to syringe blockage. In a blinded review of the data and in consultation with the SRC, it was decided that partial injections will be excluded from the primary safety analysis and subjects who experienced any partial injection will be excluded entirely from the secondary pain score analysis. Detailed information regarding the partial injections and the impact on study conduct as well as analyses are documented in Section 8.1.

Any other decision to exclude subjects or data points from this analysis set (e.g. due to important protocol deviations) will be made in blinded data review and documented in the CSR.

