3. INVESTIGATIONAL PLAN

3.1. General Study Design

This is a randomized, crossover, single-center, Phase 1 study to evaluate and compare local tolerability following subcutaneous administration of TV-46046, diluted TV-46046, TV-46046 Placebo, and Depo-subQ 104, in 24 healthy female subjects 18 to 50 years of age. After signing the informed consent form, eligible subjects will be enrolled and receive one of each of the four subcutaneous study injections in each abdominal quadrant: 120 mg/0.3 mL of TV-46046, 60 mg/0.3 mL of 1:1 saline diluted TV-46046, 0.3 mL of TV-46046 Placebo and 104 mg/0.65 mL Depo-subQ 104 per the assigned sequence. Injections will be administered in different quadrants of the abdomen, each separated by approximately 1 hour (sufficient time to eliminate carry-over effect of pain at previous injection). Subjects will be randomized to one of 24 different injection sequences (one subject per sequence) to counterbalance potential effects of injection order or abdominal quadrant on study outcomes.

All subjects will be followed for at least 6 months after receiving their injections. Local tolerability will be assessed by evaluating ISRs at least twice on the day of the study injections (Day 0: immediately after [ie, as soon as possible but no later than 10 minutes upon removing the needle] and 1 hour [±5 minutes] after the injection), at Days 1, 3, 7, and 14; at Months 3 and 6; and at other visits, if indicated. Subjects with unresolved ISR(s) will be followed monthly through the resolution of ISR(s) or Month 18, whichever comes first.

Subjects will assess their injection site pain using an 11-point NRS (0 = no pain at all; 10 = worst pain) twice on the day of injection (Day 0: immediately after [ie, as soon as possible but no later than 10 minutes upon removing the needle] and 1 hour [± 5 minutes] after the injection). In addition, 1 hour after the fourth (final) injection subjects will provide an overall ranking of administrations from least [1] to most [4] painful. Thereafter, injection site pain will be assessed by self-reports at all subsequent visits. Adverse events and concomitant medications will be recorded throughout the study. Vital signs and weight will be measured at baseline, Month 6, and study exit. The assessments and procedures performed during each study visit are detailed in Table 1 and Section 3.4.

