8. STATISTICS

This section describes statistical analyses of primary and secondary objectives as foreseen at the time the protocol was written. Further details will be described in a separate statistical analysis plan which will be approved prior to unblinding of study statisticians. Any additional analyses or changes to planned analyses will be fully disclosed in the clinical study report. All statistical analyses will be performed using SAS[®] software Version 9.4 or later. All tests and comparisons between treatment groups will be conducted at the two-sided 0.05 significance level, with no adjustment for multiple comparisons.

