8.1. Sample Size and Power Considerations

The study size of 24 subjects, each of whom will receive all four treatments (one per abdominal quadrant), will provide at least 80% power to detect differences in the rates of ISRs among groups of the magnitude (>40%) observed in recent non-comparative studies of TV-46046 and Depo-subQ 104 (see Table 3). Although not designed to obtain precise estimates of less frequent ISR rates (eg, injection site discoloration [hypopigmentation]), there is a high (>90%) probability of detecting one or more specific ISR types per treatment if the true rate of such events is at least 10%. No randomized subjects will be replaced. However, if more than two subjects fail to receive all four injections or discontinue before Month 6, then additional subjects may be enrolled to help ensure that there are at least 22 subjects who complete the treatment sequence and are evaluable for at least 6 months.

	Injection Pain	Redness	Injection Site Discoloration (Hypopigmentation)	Any Adverse Event	Reference
TV-46046 (Study #TV-46046-WH- 10075; IND 126249)	8/12 (66.7%)	9/12 (75.0%)	2/12 (16.7%)	9/12 (75.0%)	Ongoing PK/PD
Depo-subQ 104 (Study #702179; IND 127097)	3 /18 (16.7%)	1/18 (5.5%)	0/18 (0%)	2/18 (11.1%)	Ongoing PK/PD

Table 3:ISR Rates (per injection)

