#### 2.5. Sample Size and Power Considerations

The study size of 24 subjects (N=24) will provide at least 80% power to detect differences in ISR rates of the magnitude (>40%) observed in recent non-comparative studies of TV-46046 and Depo-subQ 104. Although not designed to obtain precise estimates of less frequent ISR rates (eg, injection site discoloration [hypopigmentation]), there is a high (>90%) probability of detecting one or more specific ISR types if the true rate of such events is at least 10%. No randomized subjects will be replaced. However, if more than two subjects fail to receive all four injections or discontinue before Month 6, then additional subjects may be enrolled to help ensure that there are at least 22 who complete the treatment sequence and are evaluable for at least 6 months. The

Local Tolerability Study - Contraception Statistical Analysis Plan Version 2.0 TV46046-WH-10147 /1191167 additional subjects will be assigned new randomization numbers, and will not re-use the randomization numbers from subjects who did not received all 4 injections.

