# 6.3. Injection Site Pain

NRS pain scores for assessments on the day of injection (Day 0) will be summarized by treatment group in frequency tables, separately for pain measured immediately after injection and at 1 hour after injection. If an appropriate distribution of pain scores can be identified in blinded review (e.g., negative binomial or Poisson), then generalized linear models with exchangeable working correlation structure to account for correlated data will be used to compare treatment groups. The analysis model will only include effects of treatment, but exploratory analyses will be performed to assess effects of injection order, age, and race. If the dispersion of NRS scores is not amenable to parametric regression methods, then rank-order, permutation tests will be used to compare treatment groups (excluding any subjects who did not receive both injections being compared).

Approximately 1 hour after completing their sequence of the four treatments, each subject will also be asked to rank the injections according to overall pain from least [1] to most [4] painful. The ranking of treatment group pain will be summarized in bar charts and frequency tables, restricted to subjects who received all four injections. Differences in ranking of most painful injection will be assessed using an exact multinomial test for homogeneity across groups. If a subject cannot rank all of her injections from least to most painful, or cannot uniquely identify which injection was most painful, then her responses will be appropriately weighted across groups (e.g., if a subject ranks all 4 treatments as equally most painful, then that subject will contribute a score of 0.25 to each group when assessing distribution of most painful injection).

The proportion of subjects with unsolicited reports of injection site pain at one or more follow-up visits after Day 0 will be tabulated and compared between treatment groups using exact, pairwise McNemar tests.

Listings of pain score data will include subjects who received partial injections.

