# 8. CHANGES TO ANALYSES SPECIFIED IN PROTOCOL V1.0

# 8.1. Changes from V1.0 of SAP, prior to interim analysis

In consultation with the SRC and in a completely blind data review, the decision was made on April 26th 2019 to enroll 3 additional subjects because 3 of the planned total of 24 received only partial injections of one of the drugs. Based on this consultation, the decision was made to exclude partial injections from the primary safety analysis and to entirely exclude subjects who experienced a partial injection from the secondary pain score analysis. All subjects, regardless of any partial injections, remain included in the assessment of overall safety per section 1.2.2.2. Demographic data will be summarized for both the Treated Analysis Set and the subset of subjects who received no partial injections of drug.

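### One partial injection costs a woman all her pain ratings, and no sensitivity analysis returns partial injections to the primary ISR or NRS comparison

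*SAP*

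**What the plan says.** SAP section 3 defines one analysis set, women given at least one of the four injections, and then makes two exclusions because of syringe blockages. For ISRs, "partial injections will be excluded from the primary safety analysis", and SAP 6.1 confirms that the unit removed is the injection. For pain, "subjects who experienced any partial injection will be excluded entirely from the secondary pain score analysis", so the unit removed is the woman. SAP 8.1 gives the background: "3 of the planned total of 24 received only partial injections of one of the drugs". Three women were added, and both rules were set in a blinded review with the Study Review Committee before the interim analysis.

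The partial injections remain in the reporting. SAP 6.2 lists their ISRs and describes them with overall safety. SAP 6.3 keeps the affected women in the pain listings. SAP 6.4 counts every treated woman in the adverse event summaries and uses Fisher's exact test to compare events that can be tied to one site, such as ISRs that qualify as adverse events.

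Other parts of the plan are more sparing with data. The permutation fallback for pain in SAP 6.3 works by pair, "excluding any subjects who did not receive both injections being compared". SAP 4.3.1 uses whatever data a withdrawing woman has provided. Protocol 3.1 describes the interval of about an hour between injections as "sufficient time to eliminate carry-over effect of pain at previous injection".

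**The concern.** There are two related points.

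**Pain scores.** The SAP gives no reason for removing the whole woman for pain when it removes only the injection for ISRs. If an hour clears pain carry-over, a blocked syringe in one quadrant does not invalidate ratings from the other three, and ratings given before the blocked injection cannot be affected by it at all. The result is odd: a woman who missed an injection altogether stays in the Treated Analysis Set with her other scores, while a woman who received part of one loses every score. Only the four-way ranking needs all four injections.

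**ISRs.** Blockage occurs after randomisation and could depend on the product. The four treatments differ in concentration and delivery: 400 mg/mL, 200 mg/mL and vehicle through a 23G needle, against 104 mg in 0.65 mL (160 mg/mL) through a 26G needle. Blinded review prevents selective exclusion, but it does not remove bias if blockage depends on formulation. A sensitivity analysis would show whether the exclusion matters, and none is planned for the primary comparison.

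**Working it through.** **Plan's own figures.** SAP 2.5 says "The study size of 24 subjects (N=24) will provide at least 80% power to detect differences in ISR rates of the magnitude (>40%) observed", and gives more than 90% probability of seeing a reaction whose true rate is 10%. Protocol section 8 sets the level: "All tests and comparisons between treatment groups will be conducted at the two-sided 0.05 significance level, with no adjustment for multiple comparisons".

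- Detection: 1 − 0.9^24 = 0.920, so the claim reproduces.
- Power with 24 women at the rates in protocol Table 3 (TV-46046 against Depo-subQ 104), by exact two-sided McNemar test and assuming independence within a woman: pain 8/12 v 3/18, 0.916; redness 9/12 v 1/18, 1.000; any adverse event 9/12 v 2/18, 0.996. The claim reproduces at these differences. At exactly 40 points it depends on base rate and correlation, which the documents do not give (for example 0.80 at 50% v 10%).

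**Records removed.** Assume 24 + 3 = 27 women, four injections attempted in each, and one partial injection in each of three women.

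- Injections attempted: 27 × 4 = 108. Complete: 108 − 3 = 105.
- ISR rule: 3 of 108 removed (2.8%).
- Pain rule: 3 × 4 = 12 of 108 removed (11.1%). Of these, 3 × 3 = 9 are complete injections, and 9/105 = 8.6%.

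**Precision for pain.** Take the standard error of a within-woman contrast as proportional to 1/√(pairs). The SAP rule leaves 24 pairs for every contrast, if the added women had complete injections. If only the partial injection were excluded:

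- All three partials in one product: the three contrasts among the other products have 27 pairs, and √(27/24) = 1.061, so the SAP rule makes their standard errors about 6% wider. The three contrasts with the blocked product stay at 24 pairs.
- Three different products: contrasts have 25 or 26 pairs, giving √(25/24) = 1.021 or √(26/24) = 1.041.

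**ISR rates.** Suppose all three partials were one product, with none or all of those sites reacting. The observed counts are illustrative.

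- 12/24 (50%) becomes 12/27 to 15/27 (44% to 56%).
- 2/24 (8.3%) becomes 2/27 to 5/27 (7.4% to 18.5%).
- Chance that three excluded sites hold at least one event, assuming independent women: 1 − 0.9³ = 27% at a true rate of 10%, and 1 − (10/12)³ = 42% at 2/12, the hypopigmentation rate in Table 3.
- Detection at a 10% rate with 27 rather than 24 injections: 1 − 0.9^27 = 0.942 against 0.920.

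**What the adverse event analysis catches.** Protocol 5.2.1 counts redness or swelling as an adverse event at 5 cm or more in diameter or with more than minimal interference with activities, and localised itching when it needs at least 48 hours of treatment. The primary endpoint in SAP 1.1.2 is any ISR other than pain. A smaller patch of redness at a partially injected site is therefore listed and described, but enters no between-group comparison. Discoloration has no such threshold in that section, so whether it reaches the Fisher comparison depends on whether it is recorded as an adverse event.

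**The case against.** The strongest reply is that the exclusions are a reasoned choice, made blind and written into the SAP. The trial compares fixed doses and includes the dilution to look for dose dependence. Counting an incomplete dose under its product would blur exposure and could make that product look better tolerated. Women with a full sequence give balanced within-woman contrasts. This argument stands for the primary ISR rule, which should be kept. It does not explain why complete injections in the same women are dropped for pain.

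It can also be said that the carry-over statement concerns spacing in general, and that the pairwise rule belongs to a fallback test and to injections not received. Neither text governs partial injections. That is fair: together they show that the whole-woman rule sits badly with the plan's reasoning, not that it breaks a stated rule.

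Three stronger readings should be set aside.

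- A reader might infer that partial injections leave the analysis altogether. SAP 6.2, 6.3 and 6.4 show otherwise.
- A reader might infer that the trial falls short of its planned size. With three women added, 24 with four complete injections remain if the additions were complete. This equals the plan and exceeds the floor of 22. The 6% is measured against 27 women, not against the plan.
- A reader might infer that reactions to a particular product were removed. The documents do not name the blocked product, and the phrase in SAP 8.1 can mean one injection per woman or the same drug in all three.

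The ISR shift is also small beside the sampling error: the exact 95% interval for 12/24 is already about 29% to 71%. It matters more for uncommon reactions.

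**Conclusion.** The point holds in a limited form. The pain rule discards nine valid ratings of 105 without a stated reason and differs from the ISR rule. No pre-specified analysis repeats the primary ISR comparison or the NRS comparison with partial injections included, and ISRs below the adverse event threshold at those sites are never compared between groups.

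The size is modest: standard errors up to about 6% wider than with all 27 women for some pain contrasts, and at most three reactions missing from one product's ISR rate. Both maxima require all three partials to be one product, which is an assumption. All counts assume 27 women with four injections attempted and one partial injection in each of three. Nothing here shows bias in the planned comparison. What is missing is the analysis that would show whether the exclusion matters. It should be specified before database lock, because SAP 2.6.2 treats analyses not identified in the final approved SAP as exploratory.

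**What to change.** In SAP 3, 6.1, 6.3 and 8.1:

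1. Exclude only the partial injection from the NRS models, as for ISRs. Keep whole-woman exclusion for the four-way ranking only, and say which rule applies to follow-up pain reports, since the SAP does not define how far its term for the pain analysis reaches.
2. Keep the primary ISR rule as it is.
3. Pre-specify one sensitivity analysis of ISRs and NRS scores on the full Treated Analysis Set, with partial injections counted under the drug received.

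The cost is a few sentences of SAP text and one extra run per outcome. Clusters become slightly unbalanced, which generalized estimating equations handle. The sensitivity analysis must be read knowing that a partial dose may understate reactions, so it supports the primary ISR result and does not replace it.

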# 4. GENERAL ISSUES FOR DATA ANALYSIS

#### 4.1. General

Descriptive statistics for continuous variables will include the number of observed values, the mean, standard deviation (SD), median, minimum, and maximum values. For categorical variables, the number and percentage of subjects with a specific level of the variable will be presented.

All reported p-values will be assessed for statistical significance at the two-sided 0.05 level, and all confidence intervals (CIs) will be computed at the two-sided 95% coverage level.

#### 4.2. Specification of Baseline Values

The baseline values for any measurement is the last value obtained prior to injection of any study drug.

## 4.3. Handling Withdrawals and Missing Data

#### 4.3.1. Discontinuation and Missing Data

Per protocol, subjects who are discontinued from the study after being randomized (regardless of reason) will not be replaced. However, if more than two subjects fail to receive all four injections or discontinue before Month 6, then additional subjects may be enrolled to help ensure that there are at least 22 subjects who complete the treatment sequence and are evaluable for at least 6 months.

Local Tolerability Study - Contraception Statistical Analysis Plan Version 2.0 TV46046-WH-10147 /1191167 For any subject who withdraws prematurely from the study, all available data up to the time of discontinuation will be included in relevant analyses. Except as noted in Section 4.3.2, missing data will not be estimated or imputed.

#### 4.3.2. Imputed Date

If missing event dates are needed to compute durations of outcomes, the following rule will be applied:

• If the month and year are known, but the date is missing, the earlier of a) the 15th or b) the last day of the month the event could possibly have occurred will be used.

Other imputation rules may be required on a case-by-case basis, as determined in blind review of missing outcome data by the coordinating investigator or other delegated staff member. If these rules are defined after the approval of the SAP, they will be documented in the CSR.

#### 4.4. Study Days and Visits

The start of treatment (day 0) is defined as the date on which a subject receives a dose of study drug. The study day on which an event occurs or an outcome is assessed will be calculated as the date of the event or outcome, minus the date of treatment initiation; a negative study day indicates an event prior to study drug administration.

# 5. STUDY POPULATION

## 5.1. General

The study will enroll healthy women 18 to 50 years of age, inclusive, who are at low risk of pregnancy and have no skin disorders or skin allergies. The set of randomized subjects who receive at least one injection will be used for all study population summaries, unless otherwise noted.

## 5.2. Subject Disposition

The numbers of subjects screened and randomized, number of subjects who failed to receive all four injections, number of subjects who received partial injections, and scheduled study visits (days 0, 1, 3, 7, 14; months 3 and 6) completed will be tabulated in a frequency table. The

Local Tolerability Study - ContraceptionStatistical Analysis Plan Version 2.0TV46046-WH-10147 /1191167numbers and percentages of subjects who complete the study or discontinue early (overall and byreason) will be summarized as well. Reasons for early withdrawal will be listed.

#### **5.3.** Demographics and Baseline Characteristics

Demographic and baseline characteristics (age, marital status, education, and race) will be summarized for the Treated Analysis Set and the subset of subjects who received no partial injections of any drug. All data reported by the subjects in the Treated Analysis Set will be listed.

For continuous variables, descriptive statistics will be provided. For categorical variables, subject counts and percentages will be provided. Categories of missing data will be presented if necessary.

## 5.4. **Protocol Deviations**

Protocol deviations will be reviewed during a blinded data review by the Coordinating Investigator or other designated staff, and any analysis decisions due to these deviations will be documented prior to database lock and unblinding. Important protocol deviations captured on CRFs will be listed.

## 5.5. Treatment Compliance

For purposes of the SAP, perfect treatment compliance is defined as having received all four injections. Subjects with less than full compliance will be listed with reasons.

## 5.6. Medical History

Pre-existing medical condition data will be summarized in tables or listings.

## 6. SAFETY ANALYSIS

#### 6.1. General

Safety data will be summarized for all treated subjects. However, primary safety analyses of ISRs will exclude incomplete (partial) injections, and secondary analyses of pain scores will exclude subjects who experienced a partial injection, per Section 3. Results of all safety assessments, including local tolerability, AEs, injection site pain, change in vital sign and body weight, and use of CMs will be tabulated with descriptive statistics and/or presented in data

Local Tolerability Study - Contraception Statistical Analysis Plan Version 2.0 TV46046-WH-10147 /1191167 listings. Only outcome and event types that can be ascribed to a particular treatment (e.g., ISRs or injection site pain occurring in a particular quadrant of the abdomen) will be summarized by treatment group.

